Two overnight sleep studies will be performed approximately 1 week apart: a placebo night and a Atomoxetine-Oxybutynin (ato-oxy, 80-5 mg PO) night, in double-blinded randomized control design. For each night, the subjects will arrive at the sleep laboratory at approximately 7:00pm. A physician will complete a complete physical and medical history. The placebo or ato-oxy will be administered 30 minutes before lights out. At least 15 minutes of quiet wakefulness will be recorded to quantify the subject's awake EMG_{GG} activity. Subjects will then be allowed to fall asleep during which we will assess EMG_{GG} activity throughout the rest of the evening (see below for details).

DETAILED PROTOCOL (version approved 6/26/2017)

Measurements and equipment:

Subjects will be instrumented with standard polysomnography (PSG) recording sensors. Sleep stage and arousals will be measured with electrodes pasted on to the scalp, face, chin and chest (EEG, EOG, EKG, chin EMG). Paste-on EMG electrodes will be placed over the anterior tibialis muscle to detect leg movements. Respiratory effort belts will be placed around the chest and abdomen to measure breathing movements. Oxygen saturation will be measured continuously with a pulse oximetry probe placed on either the fingertip or earlobe. Snoring will be detected with a small microphone positioned over the suprasternal notch. Body position will be recorded with a sensor taped to the thoracic belt. Each of these devices is standard for diagnostic PSG and should not be uncomfortable.

One nostril and the back of the throat will be anesthetized with 4% lidocaine; only 2–3 ml (80–120 mg) of lidocaine is used. One small, flexible pressure-tipped catheter (Millar) will then be inserted through the anesthetized nostril until the tip of the catheter is located just above the epiglottis (or in the esophagus) by visual inspection through the mouth. This catheter is used to assess upper airway negative pressure and to calculate airflow resistance both awake and during sleep. In case of an esophageal catheter, after the visual inspection of the mouth, the patient will be required to swallow several times and the catheter will be advanced slowly to the lower third of the esophagus.

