Electromyogram activity from the genioglossus (EMG_{GG}) muscle (a major upper airway dilator muscle) may also be recorded using unipolar intramuscular electrodes as described in our previous studies (1, 23, 24). Two 25 gauge needles containing 30 gauge, Teflon-coated stainless steel wires are inserted into the muscle after topical anaesthesia with 4% lidocaine. A maximum of 2 mls of lidocaine will be used for needle insertion. If the patient cannot tolerate needle insertion once the maximum dose of lidocaine has been applied, then the procedure will be stopped. The needle is immediately removed leaving the wire in place. Both electrodes are referenced to a single ground producing a bipolar recording. GG needle placement is as follows: The muscle is approached through the floor of the mouth with each needle being inserted about 3-5 mm lateral to the frenulum and about 12-15 mm into the body of the genioglossus near its insertion into the mandible. Once the electrodes are placed, the EMG signal is amplified, rectified, and integrated on a moving time average basis with a time constant of 100 msec (CWE Incorporated).

Tests performed during wakefulness.

The patients, with the described monitoring equipment in place, will undertake two tests before going to sleep for the night, although some of the testing may not be performed in all subjects depending on availability of equipment, scheduling issues and willingness of the subject to undergo all of the testing.

Upper airway muscle activity during wakefulness

The subject will be asked to perform several maneuvers to assess the activity of the GG during wakefulness. The maneuvers include a maximal tongue protrusion, inspiration against a closed airway, swallow and maximum voluntary ventilation. Each of these maneuvers will be repeated 3 times.

After these test during wakefulness, the subjects will be given ato-oxy (80-5 mg PO) /placebo to take and the patient will be asked to sleep in the supine position for as much time as possible.

As much data will be recorded from NREM and REM sleep as possible over the night. Following completion of the study, all equipment will be removed, and the subject will be able to sleep in the laboratory free from equipment for the rest of the night. Alternatively, if the subject feels alert enough to leave, they may do so.

Data Analysis:

DETAILED PROTOCOL (version approved 6/26/2017)

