Sleep stages, arousals and respiratory events will be scored by a registered polysomnographic technologist blinded to the treatment allocation according to the American Academy of Sleep Medicine recommended criteria.

Muscle activity will be quantified using standard procedures described in our previous studies (1, 23, 24). Briefly, the raw EMG_{GG} signal will be rectified and smoothed with a 100 msec window. The peak phasic, as well as tonic, activity of the smoothed signal will be identified for each breath. Data from quiet wakefulness (free of swallowing and movement artifacts) will be averaged to determine the peak phasic and tonic activities during this state. The same will be done for stable NREM and REM sleep (free of arousals and other artifacts). Pharyngeal muscle responsiveness will be determined by calculating the slope and intercept of the esophageal pressure versus muscle EMG relationship.

Reimbursement

Subjects will receive \$100/night for participation in each overnight study (TOTAL = \$200). Reimbursement for parking expenses will be provided.

If the subjects will repeat a part or the entire protocol because of insufficient data collection, they will be reimbursed \$100 for any extra night.

If the subjects will take part to the additional nights on atomoxetine and oxybutynin alone, they will be paid \$100/night (total \$400).

VI. BIOSTATISTICAL ANALYSIS

Sample size: Based on previous data from the study of the noradrenergic drug desipramine in OSA patients, 20 patients will enable us to detect a reduction in AHI of $50\pm75\%$ (80% power, alpha 0.05), primary outcome. 20 patients will also enable us to detect a $100\pm150\%$ increase in genioglossus activity (80% power, alpha 0.05), secondary outcome. Accounting for a 20-50% failure rate of these kind of physiology studies we anticipate that we may need to enroll up to 30 patients to conclude the study

Variables of interest will be compared using a Wilcoxon matched-pairs signed rank test, with a p-value <0.05 considered statistically significant. To compare the effect of placebo, ato-oxy, atomoxetine alone and oxybutynin alone in the participants who will perform 4 study nights, we will use the Friedman's test with a post-hoc analysis (Wilcoxon) in which each treatment will be compared to placebo; the post-hoc analysis will be conducted with Bonferroni correction (p-threshold=0.017).

VII. RISKS AND DISCOMFORTS

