We believe that the risks associated with participation in this study are minimal. All study procedures have been conducted in our laboratory without serious incident. Anticipated risks and discomforts are listed below:

1. The equipment used for assessing sleep (paste on electrodes) is standard and poses no risk. The electrodes may be mildly uncomfortable and could cause some sleep interruption. Thus subjects may feel somewhat tired the day following this study.

DETAILED PROTOCOL (version approved 6/26/2017)

2. Pharyngeal/esophageal Pressure Catheter: Inserting the pressure catheter through the nostril and into the pharynx may be uncomfortable and could cause gagging or even vomiting. The anesthetized and fasting state substantially reduces the risk of discomfort or complications. As the subject will have a catheter in his/her pharynx and a nasal mask in place, the risk of aspiration must be considered. However, this has never been encountered after hundreds of similar studies. The catheter, once in place, does not gag the subject and the mask can easily be removed. Overall, the risk of aspiration is minimal.
 - i. Lidocaine. If the subjects have any history of lidocaine allergy, they will be excluded from the study. Excessive use of lidocaine can cause seizures, but this is reported with much higher doses than will be utilized in this study. However, subjects will be informed that lidocaine has an unpleasant taste.
3. Intramuscular EMG Determination: Needle insertion may be painful although the mucosa is topically anesthetized with lidocaine. We have found this pain to be similar to venipuncture and well tolerated. Discomfort is minimal once the needle is removed and the wire is left in place. A small amount of bleeding and/or a small bruise may occur. Both the needles and wires are sterilized. However, intramuscular or surface infection could occur, as it is impossible to sterilize the inside of the mouth. We have never encountered this problem or heard of it occurring elsewhere. There may be some residual soreness in the tongue for several hours after the wires are removed.

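### Does the plan leave it unclear who contributes to the genioglossus EMG and muscle-responsiveness analyses?

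*Combined protocol and SAP*

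**What the plan says.** Section II (Specific Aims) names the effect of the combination on both AHI and genioglossus EMG during sleep. Under Protocol in section V the commitment for the sleep period is firm: "we will assess EMG_{GG} activity throughout the rest of the evening". Under Measurements and equipment in the same section it is looser. The signal "may also be recorded using unipolar intramuscular electrodes", and a tolerance rule follows: "If the patient cannot tolerate needle insertion once the maximum dose of lidocaine has been applied, then the procedure will be stopped".

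Section VI gives one number, 20 patients, for two outcomes: a 50±75% reduction in AHI (primary) and a 100±150% "increase in genioglossus activity (80% power, alpha 0.05), secondary outcome". It then adds: "Accounting for a 20-50% failure rate of these kind of physiology studies we anticipate that we may need to enroll up to 30 patients". Variables of interest are to be compared with the Wilcoxon matched-pairs signed rank test.

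Section V describes one pressure catheter, advanced through the nostril "until the tip of the catheter is located just above the epiglottis (or in the esophagus) by visual inspection through the mouth". The Data Analysis part of section V then says: "Pharyngeal muscle responsiveness will be determined by calculating the slope and intercept of the esophageal pressure versus muscle EMG relationship". Section VII (Risks and Discomforts) remarks: "As the subject will have a catheter in his/her pharynx".

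Section IV lets the investigators ask a participant to repeat all or part of the study when the data are insufficient. It also makes the offer of two single-drug nights depend on improvement in both EMG and OSA severity.

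**The concern.** Three things look unsettled on a first reading.

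- **Is EMG recorded in everyone?** It is optional in one place and definite in others, although it is the powered secondary outcome.
- **Are the 20 patients in the secondary power statement patients with EMG on both nights?** If participants with AHI but no paired EMG used up the 20, enrolment could end with 20 AHI pairs and fewer EMG pairs. The secondary comparison would then have less than its stated power.
- **Who has a responsiveness slope?** The slope needs esophageal pressure, but the catheter may lie above the epiglottis. No rule says who gets which site, or that a participant's two nights must match. A reader of the results might not be able to tell a planned subset from lost data.

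At stake are the power of the secondary outcome and the readability of a mechanistic measure. The primary outcome is not involved.

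**Working it through.** **Inputs (section VI).** Genioglossus activity: 100% increase, ±150%, 20 patients, 80% power, alpha 0.05. Two assumptions are needed: the ± figure is the standard deviation of the paired change, and the test is two-sided. The documents state neither.

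**Reproducing the plan's figure.** The standardised paired effect is d = 100/150 = 0.667. Power of a paired t-test comes from the noncentral t distribution with n − 1 degrees of freedom and noncentrality d√n. For n = 20 the noncentrality is 0.667 × √20 = 2.98, and power is 80.7%. The simulated Wilcoxon signed rank test (normal differences, 10,000 runs) gives 78.9%. The normal approximation, ((1.960 + 0.842)/0.667)² = 17.7, gives 18 pairs. A two-arm formula gives 36 per arm and does not fit. The stated figure is therefore a paired calculation on 20 complete pairs.

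**What the 20 must mean.** A matched-pairs test can use only participants with a value on both nights. Applied variable by variable, it makes the EMG set the EMG pairs and the AHI set the AHI pairs. A participant without EMG drops out of the EMG comparison and stays in the AHI comparison. Section VI gives 20 as the number needed for detection and then adds an allowance for failed physiology studies. The natural reading is 20 analysable patients, with failed physiological recordings, EMG included, covered by the allowance.

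**Size if fewer EMG pairs were obtained.** The documents give no EMG success rate, so the second and third rows are assumed illustrations.

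| EMG pairs | Paired t | Wilcoxon, simulated |
|---|---|---|
| 20 | 80.7% | 79% |
| 18 (assumed) | 76.0% | 74% |
| 16 (assumed) | 70.3% | 66% |

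Two lost pairs cost 80.7 − 76.0 = 4.7 points of power, and four cost 80.7 − 70.3 = 10.4 points.

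**How EMG would go missing.** The route the plan describes is intolerance of needle insertion. The wires must be in place for the waking tongue manoeuvres, and section V gives the study drug after those tests. That loss therefore comes before the night's dosing and cannot be caused by that night's treatment. This does not cover signal lost later in the night, for which section IV allows a repeat. Section VII also reports the insertion as well tolerated in this laboratory's experience.

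**Catheter and slope, side by side.** Section V permits two sites; its Data Analysis part defines the slope on esophageal pressure. These do not conflict. The paired slope exists where esophageal pressure and EMG are available on both nights, and nowhere else. The remark in section VII adds no inconsistency: the title of that risk item names both sites, and a catheter passed through the nose to the esophagus also lies in the pharynx.

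**The case for a change.** The best case for a change is that the corrections are nearly all wording, and that a powered secondary outcome deserves an explicit denominator. The matched-pairs test drops incomplete pairs but sets no recruitment target. The failure allowance does not say that a participant with complete AHI and no EMG counts as a failure. Repeat nights may not help someone who cannot tolerate the needle. And because the single-drug nights depend on EMG improvement, the plan does not spell out what happens when EMG is absent.

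Part of this stands. The optional and definite wordings sit awkwardly together, the 20 is not labelled as paired EMG, and no rule fixes the catheter site within a participant. But none of these leads to a wrong analysis. Stating them would record what the test and the definitions already impose. On the single-drug nights, a participant without paired EMG has not shown an EMG improvement, so on a literal reading no offer is made.

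A further argument is that 30 enrolled at the upper failure rate leaves 30 × (1 − 0.50) = 15 patients, below the 20 needed. That concerns the allowance against the enrolment ceiling. It applies equally to AHI, whose standardised effect is the same (50/75 = 0.667), and it would remain if the EMG wording were firm. It lends no weight to the present point.

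**Conclusion.** No change to the plan is needed. The gap is real but small, and analysts would fill it in the obvious way: EMG is compared in participants with EMG on both nights, responsiveness in those who also have esophageal pressure on both nights, and AHI in all with two scored nights. The secondary power statement is sound for 20 pairs (80.7% by paired t, about 79% by simulated Wilcoxon). The assumed losses of two or four EMG pairs would lower it to about 76% or 70%, with no effect on the primary comparison. Responsiveness is not a named outcome and carries no power statement.

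This rests on reading the ± figure as a standard deviation, on a two-sided test, and on taking the failure allowance to include failed EMG, which is the natural but not the stated meaning. The muscle methods are referred to earlier studies that were not available here.

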a) Obstructive Sleep Apnea Patients (n=30): Patients with OSA will be recruited from our clinical sleep laboratory at Brigham and Women's Hospital, as well as from our existing database of OSA patients. These individuals will be otherwise healthy (except for well-controlled hypertension; defined as systolic blood pressure <140 mmHg and diastolic <90 mmHg) with no active medical problems and on no medications that could affect respiration or muscle control. All will be 21-65 years of age. Both men and women will have an apnea-hypopnea index (AHI) >10 events/hr during supine NREM sleep. These individuals will be recruited to encompass a large range of AHI's (from 10 to >60/hour). Approximately 30 patients will be recruited for this protocol.

Exclusion criteria:

- Any medical condition other than well controlled hypertension.
- Any medication known to influence breathing, sleep/arousal or muscle physiology.
- Claustrophobia.
- Inability to sleep supine.
- Allergy to lidocaine or atomoxetine/oxybutynin,
- Benign prostatic hyperplasia or urinary retention, which can be exacerbated by antimuscarinic medications.
- Individuals with underlying cardiac disease, such as arrhythmias.
- Individuals taking psychiatric medications, or any of the studied medications for medical care.
- History of seizures
- History of moderate or severe renal impairment
- For women: Pregnancy.

We will consider all applicants regardless of gender, race, color, creed, or national origin.

DETAILED PROTOCOL (version approved 6/26/2017)

IV. SUBJECT ENROLLMENT

Subjects will be recruited through email, telephone, newspaper, and or bulletin advertisements. Men and women with OSA will be recruited from a pool of patients being newly diagnosed with OSA and currently followed in our outpatient clinic or by advertisement in the sleep disorders clinic. Only patients who have stated in the initial clinical questionnaire that they are interested in hearing about research studies will be contacted by phone. Should the subject be interested in the study, they can call the study physician or coordinator to inquire about study participation. We will also recruit from our existing database of research participants.

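### Enrolling 30 does not protect 80% power across the plan's own 20-50% failure range: at 50% it leaves 15 evaluable patients and about 65% power.

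*Combined protocol and SAP*

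**What the plan says.** Section VI (Biostatistical Analysis, Sample size) starts from the number needed for analysis: "20 patients will enable us to detect a reduction in AHI of" 50±75%, followed by "80% power, alpha 0.05), primary outcome". The same 20 are said to suffice for a 100±150% "increase in genioglossus activity (80% power, alpha 0.05), secondary outcome".

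The step from analysed to enrolled patients is one sentence: "Accounting for a 20-50% failure rate of these kind of physiology studies we anticipate that we may need to enroll up to 30 patients". Section III (Subject Selection) gives the same figure: "Approximately 30 patients will be recruited for this protocol". No larger enrolment number appears anywhere.

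The analysis is a within-patient comparison of two nights: "Variables of interest will be compared using a Wilcoxon matched-pairs signed rank test", "with a p-value <0.05 considered statistically significant".

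Sections IV and V also allow, and pay for, repeat nights when a patient's data are judged insufficient. They do not say how many failures this is expected to recover.

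**The concern.** The sentence presents 30 as the enrolment that accounts for failure anywhere between 20% and 50%. To have 20 patients left after a fraction f is lost, 20 must be divided by (1 − f). At 50% that doubles the number to 40. Thirty is what results from multiplying 20 by 1.5, that is, from adding 50% of the target instead of allowing for the loss of 50% of those enrolled. The plan shows no formula, so this origin is an inference, but the shortfall does not depend on it.

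At stake is the 80% power stated for both outcomes. A reader of Section VI would conclude that it holds even if half the patients fail. In a small study, a null result at that failure rate would be much less informative than the plan implies.

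**Working it through.** **Inputs**

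- Analysed patients: 20 (Section VI).
- Primary outcome: mean AHI reduction 50%, ± term 75%. I read the ± term as the SD of the within-patient change. Standardised effect d = 50/75 = 0.667.
- Secondary outcome: 100/150 = 0.667, so the same power figures apply.
- Alpha 0.05 (Section VI). Sidedness is not stated; two-sided is assumed.
- Failure range 20% to 50%; enrolment up to 30 (Section VI; also Section III).

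**Step 1: reproduce the plan's 20.** Paired t-test power comes from the noncentral t distribution with n − 1 degrees of freedom and noncentrality d√n. At n = 20 it is 80.7%; at n = 19 it is 78.5%. The smallest n reaching 80% is therefore 20, exactly the plan's figure. Other readings do not return 20: a one-sided t-test needs 16, the two-sided normal approximation needs 18 (17.66 rounded up), and a two-sample comparison needs 36 per group. This supports reading 75% as the SD of the change and alpha as two-sided. The planned signed-rank test, simulated with normally distributed differences, has about 79% power at n = 20, so the plan's 80% is close for that test too.

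**Step 2: enrolment needed to keep 20.** N = 20/(1 − f):

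- f = 20%: 20/0.8 = 25
- f = 33.3%: 20/0.667 = 30
- f = 40%: 20/0.6 = 33.3, rounded up to 34
- f = 50%: 20/0.5 = 40

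The stated 30 matches this formula at 33.3% failure. At 50% it matches only 20 × (1 + 0.5) = 30.

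**Step 3: what 30 enrolled delivers.** Evaluable n = 30 × (1 − f). The last column is the binomial probability of at least 20 evaluable out of 30, assuming independent failures.

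| Failure rate | Evaluable | Power, paired t | Power, signed-rank | Chance of ≥20 evaluable |
|---|---|---|---|---|
| 20% | 24 | 88% | 86% | 97% |
| 33.3% | 20 | 81% | 79% | 58% |
| 40% | 18 | 76% | 74% | 29% |
| 50% | 15 | 67% | 65% | 5% |

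Thirty covers the range from 20% to 33.3%, which is 13.3 of its 30 percentage points, or less than half.

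**Step 4: the loss in terms of effect.** With 15 patients the paired t-test reaches 80% power only at a standardised effect of 0.778. With an SD of 75% that is a 0.778 × 75 = 58% reduction in AHI, not the 50% the plan sets out to detect.

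**The case against.** The strongest objection is the provision for repeat nights. If the 20-50% describes failed studies before any repeat, not every failure is a lost patient. Suppose, as an illustration, that each failure is repeated once with an independent 50% chance of success. Thirty enrolled would then give 30 × (0.5 + 0.5 × 0.5) = 22.5 evaluable on average, with paired-t power of about 85%. Recovering 5 of 15 failures would restore 20. But the documents give no recovery rate and do not link repeats to the sample size. Section VI uses the failure rate to raise the number of patients enrolled, which treats it as net patient loss. If repeats are what make 30 sufficient, the plan has to say so.

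Second, AHI comes from standard polysomnography, whereas the intramuscular EMG is optional and may be abandoned if not tolerated. Failures may therefore fall mainly on the secondary outcome. That is plausible, but Section VI applies one range to the whole study. Even if AHI were spared, the 80% stated for genioglossus activity would still fail at the upper end.

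Third, 50% is the extreme. At the midpoint of 35%, 30 × 0.65 = 19.5 are evaluable and paired-t power lies between 78.5% and 80.7%, essentially as planned. This stands: the shortfall matters in the upper part of the range. But the plan names that part as accounted for.

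Fourth, the enrolment wording is tentative. It is nonetheless the only ceiling given, and Section III repeats it. A one-sided test would give 79% power at n = 15, but also 89% at n = 20, which does not fit the plan's 80%.

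**Conclusion.** The point holds. The stated enrolment of 30 secures 20 evaluable patients only if no more than one third fail, not across the 20-50% range. At 50% failure, 15 patients are expected to remain. Power for both outcomes then falls to about 65% with the planned signed-rank test (67% by paired t-test), and the chance of missing the assumed effect rises from about 20% to about 35%. At 20% failure the plan exceeds its target.

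The enrolment arithmetic needs only the plan's own figures and the reading of failure as net loss of patients. The power figures also assume that the ± terms are SDs of within-patient change and that alpha is two-sided, both supported by the exact return of n = 20. The signed-rank figures further assume normally distributed changes.

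**What to change.** Replace the enrolment sentence in Section VI with a statement such as:

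> Up to 30 patients will be enrolled. This gives 20 evaluable patients (about 80% power) if the failure rate, after any repeat nights, is no more than 33%. At 50% failure 15 would be evaluable and power would be about 65%.

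The words on repeat nights settle what the failure rate measures. If the sponsor instead means the rate before repeats, the text should say so and give the assumed recovery rate. If failure is expected to differ between AHI and genioglossus EMG, give a rate for each.

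The correction changes wording only; the cost is a less favourable power figure at the upper end of the range. Section III can stay at 30. Only if the sponsor wants 80% power at 50% failure does the enrolment figure have to change, to 40 in both sections, and that would mean up to 10 more patients.

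### Does leaving the scale of the signed-rank test unstated, when both outcomes are sized in percent, put the AHI and genioglossus comparisons at risk?

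*Combined protocol and SAP*

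**What the plan says.** All the statistical text is in section VI, Biostatistical Analysis.

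- **Sizing, primary outcome.** "20 patients will enable us to detect a reduction in AHI of" 50±75%, with 80% power and alpha 0.05.
- **Sizing, secondary outcome.** The same 20 patients are said to detect a 100±150% "increase in genioglossus activity (80% power, alpha 0.05), secondary outcome".
- **Test.** "Variables of interest will be compared using a Wilcoxon matched-pairs signed rank test, with a p-value <0.05 considered statistically significant". No scale is named for the paired difference, here or elsewhere.
- **Four-night subset.** Friedman's test across the four conditions, then Wilcoxon tests "in which each treatment will be compared to placebo", with a Bonferroni threshold of 0.017.

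Away from the sample-size paragraph, AHI is expressed in events per hour. Section III, Subject Selection, sets eligibility above 10 events per hour and says patients will be "recruited to encompass a large range of AHI's (from 10 to >60/hour").

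**The concern.** Sizing and testing seem to use different units, or at least units that are not tied together. The sample size treats percent change as the quantity of interest, so an analyst could take percent change from the placebo night as the tested variable.

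That would not be a harmless choice. The signed-rank test needs differences that are symmetric about zero under the null. If the two nights are exchangeable, swapping them reverses the sign of a raw difference and of a log ratio and leaves the size unchanged. It does not do so for percent change: a fall from 40 to 20 is -50%, and the reverse is +100%. Large ranks therefore collect on the positive side. The test leans towards an increase, which is against the drug for AHI and in its favour for genioglossus activity. The Wilcoxon post-hoc tests would share the problem. Friedman's test would not, because dividing by a patient's own placebo value leaves that patient's ranks unchanged.

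At stake would be power on the primary outcome, false positives on the secondary one, and freedom to pick the scale after seeing the data. The wide range of AHI to be recruited makes raw and relative rankings differ more.

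**Working it through.** **1. The plan's own figure.** Inputs from section VI: AHI 50/75 = 0.667 SD; genioglossus 100/150 = 0.667 SD; n = 20; alpha 0.05, taken as two-sided. The paired t-test has noncentrality 0.667 × √20 = 2.98 on 19 degrees of freedom, and its power is 80.7%. The stated 20 reproduces for both outcomes. A signed-rank test applied to normal percent changes of this size has 78.7% power. The sample size is sound.

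**2. Which scale does the text imply?**
- A matched-pairs test takes two matched values per patient. Section VI applies it to the variables of interest, which are the night values of AHI and EMG.
- The next sentence puts night values into Friedman's test and follows it with Wilcoxon comparisons of each treatment against placebo.
- A test of percent change would be a one-sample test on a derived variable that no section defines.
- Percent appears only where the expected effect is described, which is common in sample-size text and does not fix the test scale.

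The ordinary reading is the raw drug-minus-placebo difference.

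**3. Is that reading valid?** Simulation: 40,000 trials of n = 20, exact two-sided critical value (true size 4.84%), lognormal nights with equal noise on both. For log-ratio SD from 0.2 to 1.5, raw differences reject 2.2-2.7% per tail. The test holds its level.

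**4. What if percent change were tested, genioglossus null.** If 100±150% is read as a ratio with mean 2.0 and SD 1.5, its coefficient of variation is 0.75, and a lognormal ratio has log SD √ln(1 + 0.75²) = 0.668. With exchangeable nights:

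| Scale ranked | False increases |
|---|---|
| Percent change | 7.3-7.6% |
| Raw difference | 2.2-2.5% |
| Log ratio | 2.4-2.5% |

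The nominal figure is 2.5%. At the 0.017 post-hoc threshold, percent change rejects 1.7-4.6% in total across the assumed noise models, and raw differences 1.5-1.6%.

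**5. What if percent change were tested, AHI power.** The noise structure is not in the documents, so each row is an assumption (n = 20).

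| Assumed model | Raw | Percent | Loss (points) |
|---|---|---|---|
| Lognormal, mean -50%, SD 75% (log SD √ln(1 + 1.5²) = 1.086) | 99.0-99.6% | 93.9-94.1% | 5.0-5.8 |
| Gamma ratio, independent of placebo AHI | 86-87% | 86-87% | up to 0.8 |
| Normal percent change, -50±75% | 70-77% | 78-79% | -1.7 to -8.7 (a gain) |
| Median ratio 0.5, log-ratio SD 0.3 | 100% | 100% | 0 |
| Median ratio 0.5, log-ratio SD 1.0 | 77% | 50% | 27 |
| Halving, additive noise of 20/h per night | 81% | 44% | 37 |

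The first three rows match the planned 50±75%, and their losses run from about -9 to +6 points. The last three keep the halving but choose the noise freely, and the loss then runs from 0 to nearly 40. Effects smaller than planned also yield sizeable losses: at log-ratio SD 0.3, power of 75% raw against 68% percent needs a drug/placebo ratio near 0.82, an 18% reduction.

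**The case for a change.** The strongest case for acting is that the direction of the lean follows from algebra and only its size depends on assumptions. The genioglossus figure of about 7.5% is calibrated to the plan's own 100±150%, and the error favours the drug. The normal model in which percent change gains power is also unrealistic: with mean -50% and SD 75%, the share below -100% is Φ(-50/75) = Φ(-0.667), about 25%, which would mean negative AHI. The gamma model gives the placebo night no independent night-to-night error. Large losses do occur under plausible additive or count-like noise, and one sentence before unblinding would close the question.

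The asymmetry stands, and so does the criticism of the normal model. What does not follow is a fault in this plan. Every adverse figure requires the analyst to leave the usual form of the named test and use a variable the plan never defines. Even then, the power loss is measured against raw differences and not against the planned 80%: under the lognormal model matched to 50±75%, testing percent change still has about 94% power.

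Nor are raw differences best in every setting. They give up 4-6 points to a log ratio under multiplicative noise, and gain 6-16 points under additive or count-like noise. Their validity is for the null of no effect in any patient: if the drug added variability around a median ratio of 1, they too would over-reject upward (5-10% in simulation). A requirement to fix one scale would therefore be partly a preference.

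**Conclusion.** The concern does not call for a change. The scale of the signed-rank test is not written out, but the ordinary reading, raw within-patient differences between nights, is valid under the null of no effect (2.2-2.7% per tail), and the sample size of 20 reproduces at 80.7% power. Following section VI as written gives a sound primary, secondary and post-hoc analysis.

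The harm arises only if percent change from placebo is tested instead. In that case, assuming lognormal nights with log-ratio SD 0.668, false genioglossus increases would be about 7.5% instead of 2.5%. The AHI power loss would be anywhere from about 0 to 40 points at a 50% reduction, depending on noise that the documents do not fix. Stating the scale would record the method already implied and would alter neither the test nor the sample size. Percent change can be reported as a description of the effect without affecting any of this.
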